#### Statistical Analysis Plan

As we are piloting the novel Asian Mediterranean diet, the primary objective is to obtain comments and feedback on the acceptability of the ready meals from NAFLD patients. The sensory data from this study were analysed using a Kruskal-Wallis test, and a one-

way analysis of variance (ANOVA) was used with significant differences detected for p <0.05.

Information about liver enzymes (ALT, AST, Albumin, bilirubin, alkaline phosphatase, and GGT), platelet count, and lipid profile (total cholesterol, LDL, HDL, TG) will be obtained from the subjects' medical records using the most recent laboratory data. Subjects will be required to complete a semi-quantitative food frequency questionnaire (FFQ) that includes foods and beverages commonly consumed in Singapore. The aim is to assess subjects' usual dietary intake over the past 6 months and evaluate their baseline dietary intake and adherence to the Mediterranean Diet.

Data collected by collaborators will be anonymized. Recruited participants will be de-identified through a subject ID to ensure the responses are kept anonymous. Participants' identifiable information like names, contact numbers, emails, gender, race, and age will be collected and stored securely in an encrypted password-protected file. Identity of participants will be kept in a separate file from the research data. Only the study investigators will have access to this file. The files containing all research data will be password-protected and stored in project PDDS folder. Access to data will be restricted to only authorised people who are involved in this study. The data will be retained in SIT for 10 years in line with SIT Research Data Management Policy Version 1.1.

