## Study Population

We plan to recruit 30 adults diagnosed with NAFLD from the Department of Hepatology in Singapore General Hospital.

Inclusion criteria include:

- Diagnosis of NAFLD, as determined clinically by imaging evidence of hepatic steatosis on ultrasound/CT/MRI.
- Aged from 21 to 60 years old.

Exclusion criteria include:

- Secondary causes of NAFLD (e.g. medication-induced), unstable body weight (variation >5% within the preceding 3 months),
- Current use of weight loss medications,
- Other liver diseases (viral hepatitis, auto-immune or cholestatic liver disease, Wilson's disease, hemochromatosis, alpha-1 anti trypsin deficiency),
- Unstable diabetes (HbA1c >8.5%),
- Renal failure,
- Inability to provide informed consent,
- Pregnancy and lactation,
- Problems with tasting and smelling,
- Food allergy/intolerances/restrictions.

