## Study Visits Procedure

All eligible subjects will be given a participant information sheet and a consent form if they wish to participate in the study. The PI will also be available for any clarifications either through phone call or via email. With permission from the subjects, the SIT research team will message them to remind subjects of the requirements before coming for their study visits. Anthropometric data (weight, height, body mass index, waist circumference) and body composition using bioelectrical impedance will be assessed.

Recruited subjects will be invited to SIT@Dover campus tentatively in the months of Mar 2024 to Dec 2024 for two sessions of sensory evaluation test on the acceptability of the Asian Mediterranean diet (AMD) sample meals. All the ready meals will be heated up to

the required temperature before consumption. Subjects will taste a total of 14 different food items, over 2 study visits. This is to minimize taste fatigue if more than 5-7 samples are tasted at each study visit. After tasting the food items, subjects will be required to evaluate the food items tasted. A sensory evaluation form will be provided to the subjects. Subjects are required to complete the form before leaving the food tasting lab. The duration of each session is expected to take 60 minutes. Reimbursement will be given upon the completion of both study visits.

Sensory evaluation food tasting preparatory steps will involve:

1. All ready meals will be reheated to the appropriate consumption temperature when the subject arrives at SIT's food-tasting lab.
2. All trays, crockeries and cutlery will be provided. Environment settings will be standardised throughout all sessions.
3. Subject verification and registration will be carried out before subjects enter the food-tasting lab.
4. Before the commencement of the food-tasting session, subjects will be briefed on the food-tasting procedure and instructions.
5. A total of 7 food items will be served to participants and 50g of each food product will be portioned out. A pictorial illustration of the actual ready meal will be provided to the subject.
6. Subjects will be required to fill up the online food-tasting evaluation forms.
7. Throughout the tasting session, subjects will not be allowed to communicate with other subjects in the food-tasting lab.
8. Subjects will leave the food-tasting lab when they have finished evaluating all the food items.
9. Trays, crockeries, and cutlery will be collected back.

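### The tests named for the sensory data compare groups only, so on their own they cannot show whether the meals are acceptable; no estimate of the rating level is planned.

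*Combined protocol and SAP*

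**What the plan says.** The Overview sets the aim of evaluating how acceptable the diet is to people with NAFLD. The Statistical Analysis Plan repeats this for a pilot: "the primary objective is to obtain comments and feedback on the acceptability of the ready meals from NAFLD patients".

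The design has one group and no comparator. Under Study Population, "We plan to recruit 30 adults diagnosed with NAFLD". Under Study Visits Procedure, "Subjects will taste a total of 14 different food items, over 2 study visits", and ratings are recorded on an evaluation form that is not reproduced in the text supplied.

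The analysis of those ratings is a single sentence in the Statistical Analysis Plan: "The sensory data from this study were analysed using a Kruskal-Wallis test", together with a one-"way analysis of variance (ANOVA) was used with significant differences detected for p <0.05". The grouping factor is not named. No section mentions a mean, median, proportion or confidence interval for the ratings.

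**The concern.** Acceptability is a question about level: where do the ratings sit on the scale? The two named tests ask whether groups differ, presumably the 14 food items. A menu that is liked throughout and one that is disliked throughout can give the same test statistic and the same p-value.

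What is at stake is the main result of the pilot. The analysis in the plan does not produce it. The analysis that would produce it is left to be chosen after the ratings are seen: mean, median or share favourable, and per item or overall.

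**Working it through.** The plan gives no power, precision or acceptability figure, so there is no stated number to reproduce. The check has two parts: whether the tests respond to the rating level, and how precise the missing estimates would be.

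**Inputs from the documents:** 30 subjects (Study Population); 14 items per subject (Study Visits Procedure). This gives 30 × 14 = 420 ratings if all are complete.

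**Assumptions, because the documents give none:** a 9-point scale, the rating SD, and the within-subject correlation (ICC).

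**1. Response to level (exact, no assumptions needed).** Add a constant c to every rating.
- Kruskal-Wallis uses only ranks. Adding c leaves the ordering and the ties as they were, so H does not change.
- ANOVA uses deviations from means. Since (y + c) − (mean + c) = y − mean, the between-group and within-group sums of squares do not change, and neither does F.

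This holds whatever grouping factor is meant.

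**2. Illustration.** One 30 × 14 set of ratings was simulated (item means 6.5 to 8, SD 1.2, ICC 0.3, rounded and limited to 5–9). Menu B is the same set minus 4.

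| | Menu A | Menu B |
|---|---|---|
| Mean rating | 7.13 | 3.13 |
| Share at 6 or above | 92% | 0% |
| Kruskal-Wallis H, by item | 90.55 | 90.55 |
| ANOVA F, by item | 8.58 | 8.58 |

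The 0% follows from the construction, since 9 − 4 = 5. The table shows the identity at work; it does not predict this trial's results. A second simulated set, shifted to means of 3.07, 5.07 and 7.07, gave H = 10.99 (p = 0.611) and F = 0.841 (p = 0.617) all three times.

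**3. Precision of the missing estimates at n = 30.**
- Share favourable for one item, exact (Clopper-Pearson) 95% CI: 24/30 = 80%, 61.4% to 92.3%; 15/30 = 50%, 31.3% to 68.7%.
- Mean rating for one item: half-width = t(29) × SD/√30. This is 0.56 for SD 1.5 and 0.78 for SD 2.1.
- Subject-averaged overall mean: half-width = t(29) × SD × √(ICC + (1 − ICC)/14)/√30. At ICC 0.3 the root is √(0.3 + 0.7/14) = √0.35 = 0.592, giving 0.33 (SD 1.5) to 0.46 (SD 2.1). Over ICC 0.1 to 0.5 the range is 0.23 to 0.57.
- Treating the 420 ratings as independent: t(419) × SD/√420 = 0.14 to 0.20. For the same SD this is too narrow by a factor of 1.6 (ICC 0.1), 2.3 (ICC 0.3) or 2.9 (ICC 0.5). The overall interval should therefore rest on 30 subjects.

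**The case against.** The strongest reply is that this is a feedback pilot. Read literally, the primary objective is to collect comments and feedback, and completed forms achieve that. No acceptability hypothesis is stated that the tests then fail to address. Comparing 14 recipes to find those liked less is useful when a menu is being developed, and item means or medians normally accompany such tests.

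Much of this stands. A between-item comparison is a reasonable secondary analysis, and the likely consequence is a gap in the plan more than a wrong conclusion. Two things remain. The Overview says the aim is to evaluate acceptability, which is about level. And if the pilot is descriptive, description is its main analysis, which is the part not written down.

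A reader might go further and infer that the study cannot answer its question, or that no summaries will be reported. The documents do not support that. The ratings to be collected are enough to estimate level, and silence in the plan does not mean summaries will be omitted. Nor can the form be faulted: its scale, attributes and comment fields are not in the text supplied. A pass/fail cut-off is not needed for a pilot of this kind, so its absence is no defect.

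**Conclusion.** The point holds as a minor one. The only analyses named for the sensory data are unaffected by the overall rating level, so on their own they cannot show whether the meals are liked, and no section states an estimate that would. The invariance is exact and rests on no assumption. The size of the mismatch in the illustration, and the half-widths for the mean ratings, depend on the assumed scale, SD and ICC.

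The unnamed grouping factor, the lack of a rule for choosing between the two tests, and the lack of a stated way to summarise comments are specification gaps. They are worth closing in the same edit, but they add no weight to this conclusion.

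**What to change.** In the Statistical Analysis Plan, make descriptive estimation the primary analysis:

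- For each of the 14 items, report the mean (or median) rating and the share of subjects rating it favourably. Define favourable on the form's own scale before the data are reviewed.
- Report the overall score as the average of each subject's ratings.
- Give 95% confidence intervals based on the 30 subjects, not on the 420 ratings.
- Keep the between-item comparison as secondary, for ranking recipes, and name its factor.

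At a minimum, one sentence committing to per-item descriptive summaries and naming the factor would cure the core defect.

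The cost is SAP wording and a few summary rows from ratings already planned, with no extra subjects or visits. The downside is that per-item intervals are fairly wide at this sample size, as shown above, so single-item results should be read as indicative.

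### The sensory ratings are to be tested with independent-groups methods (Kruskal-Wallis, one-way ANOVA) although each of the 30 subjects rates all 14 items; if items are compared, real differences are more easily missed

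*Combined protocol and SAP*

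**What the plan says.** - **Subjects.** Study Population describes one group with no arms: "We plan to recruit 30 adults diagnosed with NAFLD".
- **Tasting.** Study Visits Procedure states "Subjects will taste a total of 14 different food items, over 2 study visits". The preparatory steps give the number per session: "A total of 7 food items will be served to participants". The subjects then rate what they have eaten: "After tasting the food items, subjects will be required to evaluate the food items tasted".
- **Analysis.** The Statistical Analysis Plan section states "The sensory data from this study were analysed using a Kruskal-Wallis test", and the sentence goes on to a one-"way analysis of variance (ANOVA) was used with significant differences detected for p <0.05".
- **Purpose.** The same section says that "the primary objective is to obtain comments and feedback on the acceptability of the ready meals from NAFLD patients".

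The section does not say which groups the tests compare, which rating they use, or when each of the two applies. No paired, blocked or mixed-model method appears anywhere in the document.

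**The concern.** Kruskal-Wallis and one-way ANOVA are tests for separate samples. Here the sensory procedure creates one factor with several levels, the 14 items, and all 14 are rated by the same people. If items are compared, independence between groups fails by design.

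Some people score everything high and others score everything low. The repeated tasting allows that variation to be removed, because each subject serves as his or her own control. The named tests leave it in the error term. The error variance is then too large for the comparison being made, the tests reject less often than 5% when the items are equal, and power is lost when they are not. A less-liked meal could be reported as no different from the others.

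**Working it through.** The plan gives no sample-size reasoning, effect size, SD or rating scale, so it has no figure of its own to reproduce. The check has two parts: the algebra, then a simulation under stated assumptions.

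**Inputs from the document.** n = 30 subjects (Study Population); k = 14 items per subject (Study Visits Procedure); significance level 0.05 (Statistical Analysis Plan).

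**Assumed inputs.** 9-point scale, mean 6.5, total SD 1.6; one item lower than the other 13 by d SD; equal correlation ρ between any two ratings by the same subject, with ρ = 0, 0.15, 0.3 and 0.5.

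**Algebra.** Write a rating as item effect + subject effect + residual, with total variance SD².

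- One-way ANOVA: expected error mean square = SD², on 14 × 29 = 406 degrees of freedom.
- Subject-blocked ANOVA: expected error mean square = SD² × (1 − ρ), on 13 × 29 = 377 degrees of freedom.
- With equal items, the expected item mean square is SD² × (1 − ρ). The blocked F ratio is therefore centred near 1, and the one-way ratio near 1 − ρ.
- The 5% critical value of F on 13 and 406 degrees of freedom is 1.74. At ρ = 0.3, exceeding it is roughly the same as the blocked ratio exceeding 1.74 / 0.7 = 2.49, which has a probability of about 0.3%. The simulation below gives 0.4%.

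**Simulation.** 10,000 trials per setting, normal subject and residual errors, rounded and clipped to 1–9. Entries are the percentage of trials with p < 0.05.

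| d (SD) | ρ | One-way ANOVA | Kruskal-Wallis | Repeated-measures ANOVA | Friedman |
|---|---|---|---|---|---|
| 0 | 0 | 4.9 | 4.6 | 4.9 | 4.9 |
| 0 | 0.15 | 1.9 | 1.8 | 4.9 | 4.7 |
| 0 | 0.3 | 0.4 | 0.4 | 5.1 | 4.8 |
| 0 | 0.5 | 0.0 | 0.0 | 5.0 | 4.6 |
| 0.5 | 0 | 32 | 28 | 32 | 27 |
| 0.5 | 0.15 | 23 | 19 | 38 | 32 |
| 0.5 | 0.3 | 15 | 12 | 46 | 39 |
| 0.5 | 0.5 | 6 | 4 | 61 | 55 |
| 1 | 0.3 | 93 | 88 | 99 | 98 |

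On an assumed 5-point scale (mean 3.7, SD 0.9), with d = 0.5 and ρ = 0.3, the four figures are 14, 11, 41 and 37%.

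**Difference detectable with 80% power** (unrounded normal ratings). For one low item the blocked noncentrality is n × d² × (1 − 1/k) / (1 − ρ).

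- At ρ = 0 both analyses need d = 0.81, where the noncentrality is 30 × 0.81² × 13/14 = 18.3.
- Blocked, ρ = 0.3: 0.81 × √0.7 = 0.68 SD. Blocked, ρ = 0.5: 0.81 × √0.5 = 0.57 SD.
- One-way ANOVA: 0.87 SD at ρ = 0.3 and 0.91 SD at ρ = 0.5.

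**A different pattern of item means.** With 14 evenly spaced means (SD of the means 0.15 of the total SD, 2,000 trials, ρ = 0.3), one-way ANOVA detects differences in 23% of trials against 62% for repeated measures, and Kruskal-Wallis in 20% against 53% for Friedman. The direction does not depend on the single-low-item assumption.

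**The case against.** **The comparison is not stated.** The study also records age, gender, race, body mass index, body composition and adherence to the Mediterranean diet. Either named test would be valid for comparing such subgroups on one value per subject. If all 14 ratings were pooled within subgroups, ignoring the clustering would tend to produce too many false positives, the opposite direction. This stands as a condition on the conclusion. However, the plan describes no subgroup analysis of the ratings, and items are the factor that the tasting procedure itself creates.

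**Little depends on the p-value.** The primary objective is feedback, no selection or success rule uses the tests, and item scores and comments are available whatever the omnibus result. An omnibus test does not show which meal is liked less. The error is also on the conservative side. All of this stands and keeps the point minor.

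**The size is assumed.** It runs from no loss at zero correlation to a large loss at 0.5, so the document supports only the direction, and that only for positive correlation. Even the blocked tests would miss a 0.5 SD difference in more than half of trials at a correlation of 0.3. Both remarks are right.

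**Visits may matter.** Ratings from one visit may be more alike than ratings from different visits. With an assumed subject variance of 0.2, a subject-by-visit variance of 0.2 and fixed item sets per visit, the false-positive rate was about 6.6% for repeated-measures ANOVA and 5.5% for Friedman (4,000 trials). The inflation is small and does not reverse the conclusion, but it bears on the choice of model.

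**Conclusion.** The concern holds, on the condition that the tests are meant to compare items. The named tests do not match a design in which every subject rates every item. With positive within-subject correlation they reject too rarely under equality and lose power. At an assumed correlation of 0.3, power for a 0.5 SD item falls from 46% to 15% (ANOVA) and from 39% to 12% (rank tests), and the difference needed for 80% power rises from 0.68 to 0.87 SD. The loss disappears at zero correlation and is small for a 1 SD difference. These sizes rest on an assumed scale, SD and correlation; the direction follows from the design. In a feedback-led pilot this is a change worth considering rather than a threat to the study.

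**What to change.** In the Statistical Analysis Plan section:

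1. State that the factor compared is the 14 items, and name the rating from the sensory evaluation form that is tested, for example overall liking.
2. Replace the two tests with one subject-blocked analysis: a Friedman test, or a mixed model with item as a fixed effect and subject as a random effect. In the mixed model, a random subject-by-visit term would allow for ratings within a visit being more alike.
3. If pairwise item comparisons are made, label them exploratory. This is a suggestion, since the plan mentions none.
4. If subject subgroups were the intended comparison, say so and analyse one value per subject or model the clustering.

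The cost is wording, with no extra subjects, visits or data. The section describes the analysis in the past tense; if that is literal, a short re-analysis of the same ratings is also needed. Friedman requires all 14 ratings, so a subject who misses a visit is dropped; the mixed model keeps that subject.
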